- Follow-up safety visit, 2 weeks post study treatment dosing (± 2 days), or upon early withdrawal.

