|--|---|---|---|---|---|---|-----------------|--|
| Vital signs ¹² | X | | | | X | X | X | Visit 4 measure both pre-dose and post-awakening from PSG |
| AE/SAE monitoring | X | X | X | X | X | X | X | |
| Study Instruction Reminder | | | | | X | | | |
| Oximeter Battery Change | | | | | X | | | |
| Prior/concomitant medication monitoring | | | | | X | X | X | |
| Inpatient Polysomnography | | X | | | | X | | |
| ESS | X | X | | | | X | | Measured at Visit 1 to determine eligibility and as efficacy outcome on PSG nights; measured evening of baseline PSG and Visit 4 PSG |
| CSSA | X | | | | | X | X ¹³ | Item 17 of the CSSA is used to assess suicidality |
| Patient Global Impression-Severity | | X | | | | X | | Measured evening of baseline PSG and Visit 4 PSG |
| Patient Global Satisfaction with Treatment | | | | | | | X | |
| Home Oximetry | | | X | X | | | | Oximeter used all at-home dosing nights |
| Delayed Word Recall Test | | X | | | | X | | Administer at similar time after awakening after each PSG |
| DSST | | X | | | | X | | Administer at similar time after awakening after each PSG |

Abbreviations: AE = adverse event; CPAP = continuous positive airway pressure; CSSA = Cocaine Selective Severity Assessment; CYP2D6 = cytochrome P450 2D6; DSST = Digit Symbol Substitution Test; ECG = electrocardiogram; EOS = end of study; ESS = Epworth Sleepiness Scale; HIV = human immunodeficiency virus; ICF = informed consent form; IRB = Institutional Review Board; IRT = Interactive Response Technology; OSA = obstructive sleep apnea; PSG = polysomnography; QHS = 1 dose taken at bedtime; SAE = serious adverse event; STOP-Bang = Snoring, Tiredness, Observed apnea, Blood Pressure-Body mass index, Age, Neck circumference and Gender criteria; WOCBP = women of childbearing potential.

- 1 Following pre-screening, participants who meet basic eligibility requirements will be screened during a visit that includes non- PSG evaluations. Participants who otherwise are eligible will be scheduled for an overnight PSG study.
- 2 If a participant discontinues from the study, all EOS procedures should be performed at the discontinuation visit, within 48 hours of the last study dose.

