7.2 Stopping Criteria

7.2.1 Individual Participant Stopping Criteria

- Incidents of abuse, diversion, or misuse of the study treatment.
- Incidents of clinical significance: hallucinations, amnesia, delusional thinking, delirium, manic symptoms, aggressive behavior, suicidality, homicidality, agitation, confusion, or convulsions/seizures.
- Participants reporting any SAE.
- Acute urinary obstruction.
- Any other AE that in the judgment of the Investigator necessitates the participant stopping to protect participant safety.

Participants discontinued from dosing will undergo end of study procedures with follow-up monitoring of the AE(s) as clinically indicated.

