8.3.1 Time Period and Frequency for Collecting AE and SAE Information

All AEs and SAEs will be collected from the signing of informed consent form (ICF) until Visit 5/EOS at the timepoints specified in the SoA ([Section 1.3](#)).

All SAEs will be recorded and reported to the Sponsor or designee within 24 hours, as indicated in [Appendix 3](#). The Investigator will submit any updated SAE data to the Sponsor within 24 hours of it being available.

Investigators are not obligated to actively seek AEs or SAEs after the conclusion of study participation. However, if the Investigator learns of any SAE, including a death, at any time after a participant has been discharged from the study, and he/she considers the event to be reasonably

related to the study treatment or study participation, the Investigator must promptly notify the Sponsor.

The method of recording, evaluating, and assessing causality of AEs and SAEs and the procedures for completing and transmitting SAE reports are provided in [Appendix 3](#).

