The Sponsor will also provide annual safety updates to the regulatory authorities and IECs responsible for the study. These updates will include information on SUSARs and other relevant safety findings.

Reporting Serious Adverse Events

The Investigator must report any SAEs to the PAREXEL Clinical Studies Safety Center within 24 hours of becoming aware of the event.

When calling to report an SAE, state that you are reporting an SAE and give the Investigator's name, your name, the telephone number where you can be reached, and the protocol number and title.

The Investigator and the Sponsor (or Sponsor's designated agent) will review each SAE report and the Sponsor/PAREXEL will evaluate the seriousness and the causal relationship of the event to study treatment. In addition, the Sponsor (or Sponsor's designated agent) will evaluate the expectedness according to the reference documents (Investigator's Brochure or US product labeling for atomoxetine or oxybutynin). Based on the Investigator and Sponsor's assessment of the event, a decision will be made concerning the need for further action.

All SAEs will be recorded from signing of informed consent until the end of the study. Serious adverse events occurring after the end of the study and coming to the attention of the Investigator

must be reported only if they are considered (in the opinion of the Investigator) causally-related to study treatment.

SERIOUS ADVERSE EVENT REPORTING INSTRUCTIONS

PAREXEL International Corporation

Clinical Studies Safety Center

The names and contact information for SAE reporting
will be provided in the Study Reference Manual.

1. Telephone the Medical Monitor/Drug Safety Specialist to inform him/her that you are faxing an SAE form. If the Medical Monitor is not available or you are calling after business hours (8:30 am to 5:30 pm Eastern time, Monday to Friday), leave a message in his/her voice mailbox.
2. Provide the Medical Monitor with the Principal Investigator's name, your name, the telephone number where you can be reached, and the protocol number and title.
3. Fax the completed SAE form and any supporting documentation within 24 hours of becoming aware of the event to the email address or fax number listed on the SAE reporting form (investigator site file).

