2 STUDY OBJECTIVES

2.1 Primary Objective(s)

1. To assess the efficacy of 3 different fixed doses of AD036 (the combination of atomoxetine and oxybutynin) vs. placebo.
2. To evaluate safety and tolerability of the combination AD036.

3 INVESTIGATIONAL PLAN**3.1 Overall Study Design and Plan**

This is a phase 2, randomized, double blind, placebo-controlled, repeat-dose, parallel arm, outpatient and inpatient, multi-center, dose finding study of the combination of atomoxetine and oxybutynin in adults with obstructive sleep apnea (OSA) documented by polysomnography (PSG).

Number of Participants and Randomization: Approximately 140 participants will be randomized to study treatment in equal ratio (1:1:1:1), at least 35 participants per arm, to 1 of 4 parallel treatment groups. At a study site, multiple randomizations may occur within a single arm in a short period of time, temporarily leaving no investigational product available for the given study arm while resupply is sent from the depot. Consequently, if a subsequent randomization is to the same study arm, that randomization number will be skipped, and the patient will be randomly allocated to the next free number in the randomization list corresponding to one of the treatments in stock at the site, i.e. “forced randomization”. Skipped randomization numbers will remain unallocated.

[figure not shown]
Treatment Groups and Duration: There will be 4 parallel treatment groups, as follows:

| Group | Atomoxetine/oxybutynin (mg) | Subjects (n) |
|-------|-----------------------------|--------------|
| 1 | 75/5 | 35 |
| 2 | 75/1.5 | 35 |
| 3 | 25/5 | 35 |
| 4 | Placebo | 35 |

Overall study duration will be up to 8-9 weeks, with up to 28 days for screening and baseline PSG. All participants will receive placebo for 2 days to establish baseline measures. Participants assigned to active treatment will subsequently receive low dose (25 mg atomoxetine/1.5 mg oxybutynin) for a 3-day dose-escalation period. Participants randomized to placebo will have a placebo run-in period.

Following the dose-escalation period, participants will receive the dose level to which they were randomized (75/5; 75/1.5; 25/5; placebo) for 7 (± 2) nights (6 nights at home, seventh night inpatient PSG). On the final night of dosing, participants will return for inpatient PSG (Visit 4). A follow-up safety visit will take place 2 weeks post study treatment dosing (± 2 days), or upon early withdrawal (figure 1).

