3.2.2 Primary Safety & Functional Endpoints

Safety Endpoints

1. The number and percentage of participants reporting Adverse Events (AEs), including the post-dosing period
2. Change from baseline in physical examination findings
3. Change from baseline in clinical laboratory testing (hematology, serum chemistry, urinalysis, other tests)
4. Cocaine Selective Severity Assessment (CSSA) results, Modified for study treatment
5. Prospective Suicidality Assessment (item 17 “suicidality” of CSSA) results

6. Change from baseline in PSG parameters: heart rate, electrocardiogram (ECG), electroencephalogram (EEG), oximetry
7. Change from baseline in vital signs, ECG

Functional Endpoints

1. Digit Symbol Substitution Test (DSST) results
2. Delayed Word Recall Test (DWRT) results

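### New-onset adverse events and end-of-study assessments reach at most 2 days past the last dose in participants who stop early, against 12–16 days in completers

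*Protocol*

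**What the plan says.** Five places fix the timing.

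- Protocol 1.3, Schedule of Activities, footnote 2: if a participant discontinues, "all EOS procedures should be performed at the discontinuation visit, within 48 hours of the last study dose". The SAP's schedule appendix (6.1) carries the same footnote.
- Protocol 1.1 (Synopsis): "Follow-up safety visit, 2 weeks post study treatment dosing (± 2 days), or upon early withdrawal". SAP 3.1 repeats it: "A follow-up safety visit will take place 2 weeks post study treatment dosing (± 2 days), or upon early withdrawal". The early visit thus replaces the two-week visit and is not added to it.
- Protocol 7.2.1: "Participants discontinued from dosing will undergo end of study procedures with follow-up monitoring of the AE(s) as clinically indicated". Anyone taken off dosing follows this path.
- Protocol 8.3.1: "All AEs and SAEs will be collected from the signing of informed consent form (ICF) until Visit 5/EOS". The same section says that investigators need not actively look for events once participation has ended.
- Protocol 10.3 (Appendix 3): SAEs after the end of the study "must be reported only if they are considered (in the opinion of the Investigator) causally-related" to treatment.

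On the analysis side, the first safety endpoint in SAP 3.2.2 is "The number and percentage of participants reporting Adverse Events (AEs), including the post-dosing period". SAP 4.10.1 tabulates numbers and percentages of participants by arm. It gives no end date for treatment-emergent events and no adjustment for length of observation.

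**The concern.** The same percentage mixes participants observed for about two weeks after dosing with participants observed for two days or less. If early stopping differs between arms, the arm with more of it has less post-dosing observation behind its figure. New post-dosing events are then under-counted there, mainly in the rows by system organ class and preferred term, by severity, and for events of special interest. The trial is meant to guide dose selection and describe repeat-dose tolerability, so between-arm comparisons of these rows matter.

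Scheduled assessments are mixed in the same way. The CSSA is there partly to detect withdrawal symptoms, and SAP 4.10.4 summarises it at Visit 5. The 12-lead ECG is taken only at screening and at end of study. Laboratory tests and vital signs are also repeated at that visit. The SAP has no rule that separates end-of-study assessments made within 48 hours of the last dose from those made at about 14 days.

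**Working it through.** **Step 1: reproduce the plan's own visit day.** The completer's last dose is on the Visit 4 PSG night, Day 12 ± 2 (Schedule of Activities and footnotes 5 and 7). Follow-up is 14 ± 2 days later (Synopsis). Then 12 + 14 = 26 and 2 + 2 = 4, giving Day 26 ± 4, exactly as scheduled for Visit 5. The Synopsis still gives the final treatment day as Day 11 ± 2. From Day 11 to Day 26 is 15 days, which does not alter the finding.

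**Step 2: compare the post-dosing windows.**

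| | Completers | Early stoppers |
|---|---|---|
| Days from last dose to end-of-study visit | 12–16 (nominal 14) | at most 2 |
| Share of the completer window | 100% | 2/16 to 2/12 = 12.5% to 16.7% (2/14 = 14.3%) |

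The completer window is 12/2 to 16/2 = 6 to 8 times as long. Between 12 − 2 = 10 and 16 − 2 = 14 days have no active collection of new events in early stoppers.

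**Step 3: what continues after the early visit.**

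- AEs ongoing at withdrawal are followed to resolution or stability, with no time limit (7.3).
- SAEs are followed to resolution or stabilization (8.3.3).
- A later SAE that the investigator learns of and considers related is reported (8.3.1).
- The CSSA is repeated by telephone one week after the end-of-study visit, but only if an item has worsened by more than 4 points (footnote 13).

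None of these actively collects a new, non-serious event that begins after the early visit.

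**Step 4: illustrative size.** The documents give neither a discontinuation rate nor a post-dosing event rate, so these inputs are assumptions: 10–20% early stopping, a 15% risk of a new event in the 14 days after the last dose, and a constant rate. The arm size of 35 is from the protocol.

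- Risk captured in 2 days: 1 − 0.85^(2/14) = 0.023.
- Risk missed per early stopper: 0.15 − 0.023 = 0.127.
- Early stoppers per arm: 35 × 0.10 = 3.5 to 35 × 0.20 = 7.
- Participants with a missed event: 3.5 × 0.127 = 0.44 to 7 × 0.127 = 0.89 per arm.
- As a share of the arm: 0.10 × 12.7 = 1.3 to 0.20 × 12.7 = 2.5 percentage points.

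An arm with 20% stopping would thus lose about 2.5 − 1.3 = 1.2 points more than an arm with 10%. If stopping were equal, the loss would be about the same in each arm at a common event risk.

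**Step 5: wider range.** With uniform onset, the expected number missed is 35 × d × q × 12/14, where d is the stopping proportion and q the 14-day risk.

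- d = 5%, q = 5%: 0.07 participants (0.2 points).
- d = 10%, q = 10%: 0.3 participants (0.9 points).
- d = 20%, q = 30%: 1.8 participants (5.1 points).

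For scale, one participant in 35 is 2.9 percentage points.

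**The case against.** The strongest reply is that the shorter window is openly stated, applies equally to every arm and costs little information. The event that led to stopping is followed without a time limit, possibly for longer than anything in a completer. Someone who stopped for an AE already counts in the any-AE row, and repeat events under the same preferred term add nothing (SAP 3.2.5.1). SAP 4.10.1 tabulates AEs leading to discontinuation directly, and its list contains no separate post-dosing table to be distorted. Any bias between arms needs unequal stopping, which is assumed. If withdrawal effects cluster in the first two days, less is lost than calculated above.

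Most of this stands, and it rules out three stronger readings that a reader might infer.

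- *Safety is least observed in those who tolerated treatment worst.* Ongoing AEs and SAEs are followed to an outcome. Early stoppers also include participants who withdrew consent, were lost to follow-up or left for other reasons (7.3).
- *Participants stopped for suicidality or seizures, and pregnancies, go unwatched after 48 hours.* A score of 3 or more on CSSA item 17 is itself an AE (8.2.5), and so is followed if ongoing at withdrawal. Families are asked to report symptoms at once, and footnote 13 provides the conditional telephone CSSA. Appendix 3 gives convulsions as an example of events usually considered serious. Pregnancy details are collected for at least 5 terminal half-lives after the last dose (8.3.5), with testing after a missed cycle or on suspicion (Appendix 4).
- *All SAE recording ends at 48 hours.* Section 8.3.1 ends routine collection at the participant's end-of-study visit. Appendix 3, however, records SAEs to the end of the study, which 4.4 defines by the last participant. The documents disagree, so the stronger statement cannot be drawn from them.

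The reply does not answer the narrower point. No provision seeks new-onset, non-serious events after the early visit, no analysis accounts for the difference in observation time, and the end-of-study assessments are made at two quite different times.

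**Conclusion.** The point holds in limited form. The difference in windows, at most 2 days against 12–16, follows directly from the documents and needs no assumption. It affects new-onset, mainly non-serious events and the timing of the end-of-study CSSA, ECG, laboratory tests and vital signs.

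The consequence is modest. On the assumptions in Step 4, fewer than one participant per arm would have a missed event. The wider range in Step 5 reaches 1.8. These figures rest entirely on assumed stopping rates, event risks and onset patterns. Distortion between arms also requires early stopping to differ between them, which the documents do not establish. This is an inexpensive improvement and not a flaw that threatens the trial's conclusions. It is worth making before the data are collected, because events nobody asked about cannot be reliably recovered at analysis.

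**What to change.** **Protocol.** Keep the 48-hour discontinuation visit. Amend 8.3.1 and footnote 2 so that AE/SAE collection runs to 14 (±2) days after the last dose for every treated participant, using one telephone contact for early stoppers who still consent. Footnote 13 already uses a telephone contact after the end-of-study visit. Reconcile 8.3.1 with Appendix 3 and 4.4 on when SAE recording ends. This changes data collection only, not dosing or clinical management.

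**SAP.** Report days of post-dosing observation by arm alongside the AE tables. Do not pool end-of-study assessments made within 48 hours of the last dose with those made at about 14 days.

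**Cost.** About a sentence each in 8.3.1, footnote 2 and the SAP, the reconciling edit, and one call per early stopper: about 4 to 7 calls per arm at the assumed 10–20%. Follow-up becomes slightly longer for those few participants. Some will decline or be unreachable, so the gap narrows but does not close.

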2.1 Study Rationale

At the doses used in the initial human studies of the AD036 combination (atomoxetine 80 mg/oxybutynin 5 mg) there was support for efficacy and safety in patients with OSA. This Phase 2 clinical study will further examine the efficacy and safety both similar and lower dose AD036 combinations versus placebo. Overall, the study is expected to provide dose selection guidance and a deeper understanding of repeat-dose safety and tolerability for the ongoing clinical development of this combination.

2.2 Background

2.2.1 Obstructive Sleep Apnea

The National Commission on Sleep Disorders Research identified sleep disorders as a major public health burden. OSA is the most common and serious of these sleep disorders and affects approximately 20 million people in the United States (US), with approximately 13% of men and 6% of women affected (Peppard et al, 2013). OSA is characterized by repetitive collapse or ‘obstruction’ of the pharyngeal airway during sleep, manifesting as repetitive episodes of hypopnea (i.e., shallow breathing) or apnea (i.e., paused breathing). These episodes of hypopnea or apnea may lead to arousal from sleep, sleep fragmentation, excessive daytime sleepiness, and/or neuropsychological impairment.

Research has shown that a number of pathogenic factors, or traits, contribute to the development of OSA (Eckert et al, 2013; Wellman et al, 2011; Wellman et al, 2013; Younes, 2003). The most important factors are the presence of an anatomically small, collapsible upper airway and a loss of pharyngeal muscle tone or responsiveness during sleep.

Long-term, OSA is associated with increased mortality and a number of adverse cardiovascular, neurocognitive, metabolic, and daytime functioning consequences (Somers et al, 1995; Nieto et al, 2000; Brooks et al, 1997; Peppard et al, 2000; Hung et al, 1990; Wessendorf et al, 2000; Hoffstein, 1994; Shahar et al, 2001; Redline et al, 1997; Findley et al, 1988).

2.2.2 Unmet Medical Need

Treatment for OSA changed little over the past 40 years, with the overwhelming majority of patients treated with positive airway pressure, the most common of which is continuous positive airway pressure (CPAP), provided by a machine that mechanically maintains an open airway. Other treatments, such as pharyngeal surgery, mandibular advancement devices, and implantable

nerve stimulators, were developed to address the anatomical predisposition to collapse; however, they have shown limited efficacy for niche populations.

While CPAP and related therapies are effective in improving sleep characteristics and oxygenation, many, perhaps most, patients find these devices uncomfortable or intolerable, and most estimates indicate that fewer than 50% of patients prescribed CPAP use it more than 4 hours per night, if at all (Weaver and Sawyer, 2010). Efforts to develop pharmacologic therapies, such as antidepressants, stimulants, and hormonal agents, for the treatment of OSA have been ongoing for at least 20 years, with no success thus far.

As many patients cannot use CPAP because they find it intolerable, this represents a significant health concern, as OSA is associated with numerous co-morbidities and increased mortality. Alternative options, such as drugs that activate the pharyngeal muscles are needed.

2.2.3 Biological Rationale

AD036 is a new fixed dose drug combination of atomoxetine and oxybutynin being developed for OSA. Atomoxetine is a pre-synaptic norepinephrine reuptake inhibitor indicated for the treatment of attention deficit hyperactivity disorder in children and adults. Oxybutynin is an antispasmodic drug that inhibits the muscarinic action of acetylcholine on smooth muscle and is indicated for the treatment of symptoms of bladder instability associated with voiding in patients with uninhibited neurogenic or reflex neurogenic bladder such as urgency, frequency, urinary leakage, urge incontinence and dysuria.

Efficacy of the combination of these 2 small molecules for the signs and symptoms of OSA has been previously evaluated in a small number of patients in National Institutes of Health-supported studies in the academic setting. The pharmacokinetics (PK) of the atomoxetine and oxybutynin combination have recently been studied in a Phase 1 clinical program sponsored by Apnimed. New research in animals improved understanding of the state-dependent neurotransmitters involved in pharyngeal muscle activation during sleep, namely that both noradrenergic and antimuscarinic processes are involved. Specifically, the loss of noradrenergic activity is now thought to play a key role in the sleep-related hypotonia of pharyngeal muscles during non-rapid eye movement (NREM) sleep and muscarinic activity is involved in rapid eye movement (REM) atonia.

Chan and colleagues (Chan et al, 2006) showed in rats that the noradrenergic antagonist terazosin substantially reduced genioglossus (a major muscle of the upper airway) activity (i.e., genioglossal electromyographic [EMG_{gg}] activity) during wakefulness and produced REM-like atonia during NREM sleep, illustrating the importance of noradrenergic mechanisms. Other

studies (Lai et al, 2001; Fenik et al, 2005) also support the notion that progressive withdrawal of noradrenergic tone, from wakefulness to NREM and REM sleep, is the major mechanism causing sleep-related pharyngeal hypotonia. While noradrenergic withdrawal is thought to be the main cause of pharyngeal hypotonia in NREM sleep, there are additional mechanisms that cause further reduction during REM sleep. Chan and colleagues (Chan et al, 2006) failed to reverse REM atonia with alpha-1 receptor agonists applied to the hypoglossal nucleus, suggesting that another, possibly inhibitory, mechanism is at work. Horner and colleagues identified this inhibitory process as muscarinic by demonstrating restoration of EMG_{gg} activity during REM sleep with the muscarinic antagonist scopolamine applied directly to the hypoglossal nucleus in rats (Grace et al, 2013; Grace et al, 2013).

However, due to the only recent identification of these processes, until now there has not yet been an attempt to stimulate the pharyngeal muscles with both noradrenergic and antimuscarinic drugs in sleeping humans. Atomoxetine (a noradrenergic) and oxybutynin (an antimuscarinic) are 2 drugs within these pharmacologic classes that have been Food and Drug Administration-approved for over 16 years and 40 years, respectively, thereby having a long history of clinical use. Atomoxetine and oxybutynin as individual drugs have well-established PK, tolerability and safety profiles, but have not previously been studied in combination.

3 Objectives and Endpoints

| Objectives | Endpoints |
|--|---|
| Primary To assess the efficacy of 3 different fixed doses of AD036 (the combination of atomoxetine and oxybutynin) vs. placebo To evaluate safety and tolerability of the combination AD036 | Primary Efficacy Endpoint 
• AHI, proportion of participants with $\geq 50\%$ reduction, PSG nights, high-dose (atomoxetine 75 mg/oxybutynin 5 mg) arm vs. placebo Safety Endpoints 
• Spontaneous adverse events, including the post-dosing period• Physical exam and laboratory testing• DSST• Delayed Word Recall Test• CSSA, Modified for study treatment• Prospective Suicidality Assessment (item 17 “suicidality” of CSSA)• PSG parameters: heart rate, ECG, EEG, oximetry• Physical exam, vital signs, clinical laboratory assessment, ECG |
| Secondary To assess the efficacy of 3 different fixed doses of AD036 vs. placebo | Secondary Efficacy Endpoints High dose vs placebo, in order: 
• Percent change AHI, high-dose arm vs. placebo• AHI in supine position, proportion of participants with $\geq 50\%$ reduction, PSG nights• Oxygen desaturation index (number of desaturations/hour $\geq 4\%$ below baseline), proportion of participants with $\geq 50\%$ reduction, at-home nights• ESS• PGI-S, OSA, PSG nights• AHI, proportion of participants with $\geq 50\%$ reduction, PSG nights, high-dose (atomoxetine 75 mg/oxybutynin 5 mg) arm vs. each low dose arm (atomoxetine 75 mg /oxybutynin 1.5 mg, and atomoxetine 25 mg/oxybutynin 5 mg). |
| Tertiary/Exploratory | Unranked Efficacy Endpoints 
• Proportion of participants with $\geq 50\%$ AHI decrease and final AHI $< 15/\text{hour}$, PSG nights• Total time with $\text{SaO}_2 < 90\%$, PSG nights• Total time with $\text{SaO}_2 < 80\%$, PSG nights• Snoring index, PSG nights• Sleep stages distribution and % of time in the various sleep stages, PSG nights• Arousal index, PSG nights• Oxygen desaturation index, low-dose run-in vs baseline, at home nights• Proportion of apneas to hypopneas |

Abbreviations: AHI = apnea-hypopnea index; CSSA = Cocaine Selective Severity Assessment; DSST = Digit Symbol Substitution Test; ECG = electrocardiogram; EEG = electroencephalogram; ESS = Epworth Sleepiness Scale; OSA = obstructive sleep apnea; PGI-S = Participant Global Impression of Severity; PSG = polysomnography; SaO_2 = oxygen saturation.

4 Study Design

[figure not shown]
